4. STUDY DESIGN

4.1 OVERALL DESIGN

This is a Phase 2 study designed to evaluate the pharmacokinetics, bioavailability, pharmacodynamics, efficacy and safety of a daily SC treatment regimen with MarzAA for bleeding prophylaxis in adult subjects with hemophilia A and B with an inhibitor. It is an open-label study, so subjects and members of the clinical study team will not be blinded to treatment. It is estimated that it will take approximately one year from when the study opens enrollment until completion of data analyses. The study will enroll a total of 12 adult male subjects with severe congenital hemophilia A or B with an inhibitor, and history of frequent spontaneous bleeding episodes (historical annualized bleeding rate [ABR] of ≥ 12), as per the individual's bleeding and treatment records. Participants will be given a single IV administration of MarzAA at 18 $\mu\text{g}/\text{kg}$ followed by single daily SC administration of MarzAA at 30 $\mu\text{g}/\text{kg}$. Dose levels may increase to 60, 90, or 120 $\mu\text{g}/\text{kg}$ as required. The H0 is that the ABR (for MarzAA) = 12 versus H1: ABR (for MarzAA) < 12.

Each subject will participate in all three phases (occurring consecutively):

Part 1a (24 hours) is intended to compare IV versus SC administration of MarzAA regarding PK, PD, and safety parameters. Each subject will receive a single IV dose of 18 $\mu\text{g}/\text{kg}$ MarzAA. PK, PD, and safety assessments will be collected pre-dose and post-dose at 5 and 30 minutes and Hour 1, 3, 6, 9, 12, and 24.

Part 1b (48 hours) is intended to compare IV versus SC administration of MarzAA regarding PK, PD, and safety parameters. After the initial 24 hours, subjects will receive a single SC dose of 30 $\mu\text{g}/\text{kg}$ MarzAA. PK, PD, and safety assessments will be done at pre-dose and repeated at Hour 3, 5, 7, 9, 12, 24, 30, and 48. During this period, subjects will be trained by appropriate study staff to self-administer a SC injection.

Part 2 is intended to (i) find the optimal dose of MarzAA for each subject, ie, the dose that prevents spontaneous bleeding; and (ii) determine the PK, PD, and safety of daily SC administration of MarzAA at the optimal dose for each subject for an extended duration, mimicking the intended SC prophylactic use of MarzAA in patients with hemophilia.

Subjects will sign an informed consent form (ICF) at the Screening Visit, prior to any study procedures. Eligibility to participate in the study will be determined by inclusion and exclusion criteria from medical history, hemophilia history, laboratory investigations and ECG. At screening, subjects will receive training

MAA-201 VERSION 2.0

and diary entry of investigational drug administration & injection site assessment, bleeding episodes & treatment, evaluation & entry of AEs & entry of PRO scales. The screening period duration may be up to 4 weeks.

At Day 1 of daily SC dosing, subjects will begin their self-administered dosing regimen. MarzAA will be self-administered by subjects daily (at approximately the same time every day), starting with a SC dose of 30 µg/kg MarzAA. At each dose, subjects will record the day and time of the SC injections in their diary. If a spontaneous bleeding episode (defined as one that is precipitated by normal ADL) occurs before the fifth daily dose, subjects will continue at the current dosing level. If a spontaneous bleeding episode occurs after the fifth daily dose, the MarzAA dose will be escalated to the next dose level. Three dose escalations are allowed during Part 2: 60, 90, and 120 µg/kg (maximum dose). At each dose level escalation, safety and PK/PD will be monitored to ensure that dose escalation to a higher dose level is appropriate. If a subject requires a third dose escalation to the fourth dose level, he will continue treatment with that dose for 50 days and complete the study, regardless if a spontaneous bleeding episode occurs during the highest treatment dose level.

The participation of each subject to all three phases is intended to reduce the number of subjects enrolled in this study.

Treatment of a spontaneous or traumatic bleeding episode: Subjects will use their current bypass regimen for any spontaneous or traumatic bleed that occurs while on study drug. If treatment for a spontaneous or traumatic bleeding episode is needed, then subjects will contact the clinical investigative team immediately to report the event, treatment dose administered, and determine follow-up plans for that event including whether to arrange for a blood specimen to be drawn (if feasible) before further administration of either study drug or the bypassing agent used for treatment. Decision whether to continue daily study drug administration will also be determined by the clinical study team after discussion with the Sponsor. See **Section 6.1.2, Dosing and Administration**, for details on dose escalation, dose de-escalation, and treatment interruption. This information will also be recorded in the subjects' diary.

Dose interruption and surgery: Daily SC study injections will be interrupted if there is a need for a surgical procedure; an event requiring extended (>48 hours) hospitalization; a thrombotic event; clinical evidence of inhibitor formation; or laboratory results suggesting an antibody may be developing.

MAA-201 VERSION 2.0

Measurements:

MarzAA antigen and activity levels and coagulation parameters will be measured at Day 1 (Pre-dose and Post-dose Hour 7), Day 3 (Pre-dose), Day 5 (Pre-dose), Day 7 (Pre-dose and Post-dose Hour 7).

If no spontaneous bleeding occurs at the first dose level in Part 2 of the study, trough antigen and activity and coagulation parameters will be measured on days 14, 21, 28, and 50 after starting their dosing regimen.

If spontaneous bleeding occurs after the fifth daily dose on a dose level, MarzAA antigen and activity levels will be measured within 6 hours of the spontaneous bleed (if feasible). Specimens for coagulation and immunogenicity testing will also be drawn.

Once it is determined to escalate to the next dose level, a pre- and 7 hours post-dose specimen will be drawn for PK, coagulation, and thrombogenicity markers on Day 7 after the dose has been escalated to estimate the new trough and peak concentrations and PD. MarzAA antigen and activity levels and coagulation parameters will then be measured (pre-dose) at Day 14, 21, 28, and 50 after dose escalation.

Immunogenicity assays: Specimens for immunogenicity testing (antibody to MarzAA, neutralizing activity, cross reactivity) will be drawn at screening, Part 1a pre-dose, Part 1b pre-dose, and during Part 2 pre-dose on Day 1, 7, 14, 21, 28, and 42, and then every two weeks until end of study.

4.2 END OF STUDY DEFINITION

The minimum duration of treatment for each subject is approximately 2 months (if no dose escalation is required) and the maximum duration is approximately 7 months (if three dose escalations are required).

Up to 4 weeks for screening period; 24 hours for the part 1a (single IV dosing and PK/PD/Safety testing); 48 hours for the Part 1b (single SC dosing and PK/PD/safety testing); and up to 197 days of daily SC dosing and a PK/PD/safety follow-up assessment 30 days after last dose. Subjects must have no spontaneous bleeding for 50 days if on the first three dose levels or complete 50 days of treatment on the fourth dose level. The end of study visit will be 30 days after the last dose of study drug treatment in Part 2.

A participant is considered to have completed the study if he has completed all phases of the study, including treatment at the same dose level for 50 days, and returned for procedures listed under end of study visit as shown in the SOA.

MAA-201 VERSION 2.0

5. STUDY POPULATION

5.1 INCLUSION CRITERIA

An individual must meet all of the following criteria to be eligible to participate in this study:

1. Confirmed diagnosis of severe congenital hemophilia A or B with an inhibitor.
2. History of frequent spontaneous bleeding episodes (historical ABR ≥ 12).
3. Male, age 18 or older.
4. Agreement to use highly effective birth control throughout the study.
5. Affirmation of informed consent with signature confirmation before any trial-related activities. (Trial related activities are any procedure that would not have been performed during normal clinical management of the subject).
6. Stated willingness to comply with all study procedures and availability for the duration of the study.

5.2 EXCLUSION CRITERIA

An individual who meets any of the following criteria will be excluded from participation in this study:

1. Receiving prophylaxis treatment.
2. Previous participation in a trial involving Subcutaneous Administration of rFVIIa (Novo Seven or MOD-5014) or any trial using a modified rFVIIa such as: NN1731 or BAY86-6150. Prior participation in a trial of LR769 or rFVIIa-FP (CSL689) is permissible.
3. Previous participation in and subsequent treatment in a clinical trial within the previous 30 days or 3-half-lives or absence of clinical effect, whichever is longer.
4. Known positive antibody to FVII or FVIIa detected by central laboratory at screening.
5. History of clinically relevant coagulation disorders other than congenital hemophilia A or B.
6. Platelet count $< 100,000$ based on screening laboratory assessments.
7. Advanced atherosclerotic disease (i.e. known history of CAD, ischemic stroke, etc.), or known DVT or considered to be at a high risk of VTE as judged by the Investigator.
8. Known or suspected allergy to trial product or related products.
9. Absolute CD4 count < 200 cells/ μL .

MAA-201 VERSION 2.0

10. Receiving IMT.
11. Compromised hepatic or renal function:
 - a. ALT and AST levels ≥ 5 times ULN
 - b. TBIL level ≥ 2 mg/dL (>35 $\mu\text{mol/L}$) unless there is a known history of GS
 - c. Serum albumin \leq LLN
 - d. Serum Cr level >1.25 x ULN
12. Inability or medical, psychosocial, or familial issues that might prevent full participation and cooperation with the procedures and requirements of the clinical trial as determined by the potential subject and physician investigator.

5.3 LIFESTYLE CONSIDERATIONS

There are no specific lifestyle considerations.

5.4 SCREEN FAILURES

An individual who does not meet the criteria for participation in this trial (screen failure) because of an out of range laboratory parameter may be rescreened.

MAA-201 VERSION 2.0

6. STUDY INTERVENTION

6.1 STUDY INTERVENTION(S) ADMINISTRATION

6.1.1 Study Intervention Description

Description and Composition of the Drug Product

MarzAA will be provided as a powder for injection, at a 4.62 mg/vial dosage strength. The drug product is supplied in a 5-mL vial that is sealed with a 20mm lyophile stopper and 20mm aluminum over-seal. To manufacture the drug product, 2.2 ml of formulated bulk drug product is filled in each vial and lyophilized. The lyophilized drug product will be reconstituted for IV and SC injection.

6.1.2 Dosing and Administration

This is an open-label study. Each subject will receive the study drug according to three phases occurring consecutively:

- In Part 1a (24 hours), subjects will receive a single IV administration of MarzAA at 18 µg /kg with assessment of PK, PD, and safety for 24 hours post-dose.
- In Part 1b (48 hours), subjects will receive a single SC administration of MarzAA at 30 µg /kg with assessment of PK, PD, and safety for 48 hours post-dose
- In Part 2, subjects will receive daily SC administration of MarzAA at 30 µg/kg with assessment of PK, PD, and safety at designated days for 50 treatment days. During Part 2, dose may be escalated to 60, 90, or 120 µg/kg, if required because of spontaneous bleeding, with assessment of PK, PD, and safety at designated days for an additional 50 treatment days.

Each subject will participate in each phase of the study.

For Part 1a and 1b, investigational product will be administered at the study site by qualified study personnel.

During Part 1b, subjects will be trained to reconstitute and self-administer the study drug. Once proficiency in drug reconstitution and SC administration has been confirmed the subject can then proceed with home administration of study treatment.

On Day 1 of Part 2 daily SC dosing, subjects will begin their self-administered dosing regimen. MarzAA will be self-administered in the morning by the subjects

MAA-201 VERSION 2.0

daily (at approximately the same time), starting with a SC dose of 30 µg/kg MarzAA. Subjects will record the day and time of the SC injections in their diary.

If a spontaneous bleeding episode (defined as one that is precipitated by normal ADL) occurs before the fifth daily dose, the subject will continue at the current dosing level.

If a spontaneous bleeding episode occurs after the fifth daily dose, the MarzAA dose will be escalated to the next dose level. Three dose escalations are allowed during Part 2: 60, 90, and 120 µg/kg (maximum dose).

On those days that the subject is required to present for a study visit during which laboratory evaluations are scheduled, he will bring his study drug for self-administration of his daily dose under observation by study team staff after pre-dose assessments are completed.

6.1.2.1 Guidelines for Dose Escalation

An escalation to the next dose level is required if a spontaneous bleeding event occurs after the fifth daily dose on a dose level. A dose escalation will not occur if the subject is on the maximum dose level of 120 µg/kg. A spontaneous bleeding episode is defined as one that is precipitated by normal activities of daily living (ADL). Subjects will use their current bypass regimen for any spontaneous or traumatic bleed that occurs while on study drug.

Three dose escalations are allowed during Part 2: 60, 90, and 120 µg/kg (maximum dose).

Safety parameters and PK/PD assessments at each dose level will be monitored to ensure that dose escalation to a higher dose level is appropriate.

The spontaneous bleeding episode must be reported to the clinical team immediately and determination of a dose escalation will be made on review of available clinical information related to the spontaneous bleeding episode and may require subsequent treatment and laboratory data, including available results from the PK/PD/safety assessments.

A decision to proceed with dose escalation will be made by the principal investigator in agreement with personnel who have Sponsor, or designee, medical oversight responsibility.

If there is disagreement amongst any of those individuals, the decision will be reviewed on an urgent basis by an independent Medical Consultant for Safety Oversight.

MAA-201 VERSION 2.0

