3.3 EXPLORATORY

- To identify potential biomarkers and determine the effect of SC administration of MarzAA on the quality of life of patients with hemophilia with inhibitors
 - Identification of biomarker(s) such as antigen levels, activity levels, or global thrombosis assay evaluation that can be used to predict or correlate with a subject's lack of spontaneous bleeding.
 - Identification of biomarker(s) such as D-dimer, F1+2, or a functional assay of the FVIIa activity that will identify or predict clinical thrombogenicity with the daily SC administration of MarzAA.
 - Identification of biomarker(s) such as D-dimer, F1+2, or a functional assay of the FVIIa activity that will identify or predict clinical thrombogenicity of daily SC administration of MarzAA when use of rescue medication is required.
 - PRO measures: European Quality of Life-5 Dimensions(EQ-5D), Visual analogue scale (VAS); Hemophilia A quality of life questionnaire(Haem-A-QoL); Hemophilia Activities List (HAL)

MAA-201 VERSION 2.0

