8.2.6.1 Day 0 Visit

If a breakthrough bleed event occurs, subjects are instructed to use their current bypass regimen for treatment and to then immediately contact the clinical investigative team to report the event, what treatment and dose was utilized, arrange for immediate follow-up, if feasible and determine follow-up plans for that event. The Day 0 Visit begins when a breakthrough bleed event occurs and includes the subsequent time until treatment resolution.

The following procedures will be performed on the Day 0 Visit:

- Medical and Hemophilia History (including that obtained from review of diary entries of bleeding episodes and treatment, AEs, and PRO scales)
- Concomitant medications
- Vital signs
- Weight
- Physical examination
- Clinical signs of thrombosis (see **Appendix A**)
- Coagulation assays: PT, aPTT, fibrinogen, FVII, FVIIa activity, and TGT
- PK: MarzAA antigen and activity
- Immunogenicity assays to FVII, FVIIa, and MarzAA
- Troponin level
- Study drug dispensing, inventory and accountability
- Dispense study drug at the escalated dose to the subject to use once the spontaneous bleeding episode has resolved. Reschedule subjects' visits for Days 7, 14, 21, 28, and 50 after dose escalation.
- Adverse events

Once the spontaneous bleeding episode has resolved, the subject will be instructed to inject MarzAA at the next dose level (60, 90, or 120 µg/mL) beginning in the morning on Day 1.

MAA-201 VERSION 2.0

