- Conduct testing for hematology and chemistry, coagulation assay, thrombogenicity markers, PK sampling
- IP compliance and proficiency confirmation
- IP dispensing, inventory and accountability
- AEs

MAA-201 VERSION 2.0

Part 2 (If spontaneous bleed occurs after the fifth daily dose)	
Day 0*	Part 2

 • Obtain medical and haemophilia history, document (including review of diary entries) • Evaluate concomitant medications, check vital signs, and weight • Conduct physical examination, check for clinical signs of thrombosis • Conduct testing for coagulation assay, PK sampling, immunogenicity assay, troponin level • Dispense study drug at escalated dose, reschedule subjects' visits for days 7, 14, 21, 28 and 50 • AEs 	
Day 7 (± 2 day)	Part 2

 • Obtain medical and haemophilia history, document (including review of diary entries) • Evaluate concomitant medications, check vital signs, and weight • Diary entry of PRO scales • Conduct physical examination, check for clinical signs of thrombosis • Conduct testing for hematology and chemistry, coagulation assay, thrombogenicity markers, PK sampling, immunogenicity assay, troponin level • IP compliance and proficiency confirmation; IP dispensing, inventory and accountability • AEs 	
Day 14, 21 and 28 (± 2 day)	Part 2

 • Obtain medical and haemophilia history, document (including review of diary entries) • Evaluate concomitant medications, check vital signs, and weight • Diary entry of PRO scales • Conduct physical examination, check for clinical signs of thrombosis • Conduct testing for hematology and chemistry, coagulation assay, thrombogenicity markers, PK sampling, immunogenicity assay (Day 14 and 28 only) • IP compliance and proficiency confirmation; IP dispensing, inventory and accountability • AEs 	
Day 42 (± 3 day)	Part 2

 • Obtain medical and haemophilia history, document (including review of diary entries) • Evaluate concomitant medications, check vital signs, and weight • Diary entry of PRO scales • Conduct physical examination, check for clinical signs of thrombosis • Conduct testing for immunogenicity assay • IP compliance and proficiency confirmation; IP dispensing, inventory and accountability • AEs 	
Day 50 (+ 3 day)	Part 2

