### 10.1 PD SAMPLING SCHEDULE

PD analysis includes following assessments

Coagulation assays	Thrombogenicity biomarkers
PT, aPTT, fibrinogen, and TGT	D-dimer, F1+2, and thrombin-antithrombin complexes (TAT)

PD sampling schedule will be specific to each part and dose administration.

Part 1a - single IV dose of 18 µg/kg MarzAA. PD sampling - predose, and post-dose at 5 and 30 minutes and Hour 1, 3, 6, 9, 12, and 24.

Part 1 b - single SC dose of 30 µg/kg MarzAA. PD sampling - pre-dose and Hour 3, 5, 7, 9, 12, 24, 30, and 48 post-dose.

Part 2 - daily SC dosing with variable dose to be determined.

PD sampling and assessments - Day 1 (Pre-dose and Post-dose Hour 7), Day 3 (Pre-dose), Day 5 (Pre-dose), Day 7 (Pre-dose). In the absence of spontaneous bleeding for the first dose level in Part 2 of the study, trough antigen and activity will be measured on days 14, 21, 28, and 50.

In case of spontaneous bleeding the PD samples will be taken within 6 hours of the spontaneous bleed and a pre- and 7 hours post-dose on Day 7, 14, 21, 28, and 50 after dose escalation.

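### The protocol draws no D-dimer, F1+2 or TAT at the Day 0 bleed visit although SAP 10.1 assumes it does, and a bleed between the fifth dose and the Day 7 draw at 60 or 90 µg/kg leaves no scheduled marker sample from that level

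*Protocol*

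**What the plan says.** **Safeguard.** Protocol 6.1.2.1 states: "Safety parameters and PK/PD assessments at each dose level will be monitored to ensure that dose escalation to a higher dose level is appropriate". The trigger is a spontaneous bleed after the fifth daily dose on a level. The decision draws on whatever clinical and laboratory results are available at the time.

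**Day 0.** Protocol 8.2.6.1 defines the visit broadly: "The Day 0 Visit begins when a breakthrough bleed event occurs and includes the subsequent time until treatment resolution". Its blood list has "Coagulation assays: PT, aPTT, fibrinogen, FVII, FVIIa activity, and TGT", MarzAA antigen and activity, immunogenicity and troponin. Appendix C gives the same content: "Conduct testing for coagulation assay, PK sampling, immunogenicity assay, troponin level". Protocol 4.1 asks for MarzAA levels within 6 hours of the bleed where feasible, then adds: "Specimens for coagulation and immunogenicity testing will also be drawn". In Protocol Table 4 the Day 0 cell for thrombogenicity markers is blank. D-dimer, F1+2 and TAT appear in none of these four places.

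**After an escalation.** Protocol 4.1 schedules "thrombogenicity markers on Day 7 after the dose has been escalated", and Table 4 has no earlier marker draw at the new level.

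**SAP.** Section 10.1 lists D-dimer, F1+2 and TAT among the PD assessments and continues: "In case of spontaneous bleeding the PD samples will be taken within 6 hours of the spontaneous bleed". SAP 3.6 instead repeats the protocol's bleed-time list of MarzAA levels, coagulation and immunogenicity. SAP 10.7 and 14, which record departures from the protocol, do not mention added bleed-time marker sampling.

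**Rescue endpoint.** One exploratory aim in Protocol 3.3 is to find biomarkers of "clinical thrombogenicity of daily SC administration of MarzAA when use of rescue medication is required". The candidates named are D-dimer, F1+2 or a functional FVIIa activity assay.

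**The concern.** Thromboembolism is an adverse event of special interest (Protocol 8.5.7). Day 0 is the visit at which the next dose level is dispensed and a bypassing agent may be on board together with MarzAA. It already includes troponin and a check for clinical signs of thrombosis, so leaving out the three thrombogenicity markers looks out of step with its purpose and with the SAP.

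Three things are at stake:

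- **Monitoring.** Some escalations can go ahead with no scheduled marker sample from the level being left, although 6.1.2.1 speaks of assessments at each level.
- **Analysis.** SAP 10.5 compares PD values taken while the subject is bleeding with those taken while he is not, and requires at least 6 observations. If Day 0 yields no D-dimer, F1+2 or TAT, the bleeding group for these markers consists only of bleeds that happen to coincide with a scheduled visit, plus discretionary samples.
- **Rescue endpoint.** The protocol ties no D-dimer, F1+2 or TAT sample to rescue use.

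**Working it through.** The plan states no figure on this point, so there is nothing to reproduce. The check compares the sampling lists and then sizes the gap.

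**1. D-dimer, F1+2 and TAT at the time of a bleed**

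| Source | Marker sample? |
|---|---|
| Protocol 4.1, Measurements | No |
| Protocol Table 4, Day 0 | No |
| Protocol 8.2.6.1 | No |
| Protocol Appendix C, Day 0 | No |
| SAP 3.6, Measurements | No |
| SAP 10.1 | Yes, within 6 hours |

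The protocol is consistent. SAP 10.1 conflicts with it and with SAP 3.6. The SAP's own copy of Table 4 could not be read reliably in the extracted text and is not used here.

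**2. Which escalations lack an on-level marker sample**

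- *30 to 60 µg/kg.* Protocol 8.2.4.2 schedules markers on Days 3 and 5, each with a +1 day window in Table 3. The Day 3 draw falls on Day 4 at the latest, before the fifth dose on Day 5. At least one multiple-dose sample is therefore scheduled before escalation is possible.
- *60 to 90 and 90 to 120 µg/kg.* The day count restarts and the first marker draw is Day 7. The trigger is live after the fifth dose, on Day 5. A bleed between the two has no scheduled marker sample from that level.
- *120 µg/kg.* There is no further escalation, so the question does not arise.

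**3. Length of the gap at 60 or 90 µg/kg**

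- Day 7 draw on time: 7 − 5 = 2 days.
- Table 4 window (+1 day), latest Day 8: 8 − 5 = 3 days.
- Appendix C window (±2 days), latest Day 9: 9 − 5 = 4 days. A draw at the early end (Day 5) would close the gap.

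**4. Chance of a spontaneous bleed in the gap, per level**

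Assume a constant rate *r* per year: P = 1 − exp(−*r* × *d* / 365). The rate of 12 is the plan's null value and 6 is its planning alternative. That either applies to spontaneous bleeds at an escalated level, and the upper value of 24, are assumptions.

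| Rate per year | d = 2 | d = 3 | d = 4 |
|---|---|---|---|
| 6 | 3.2% | 4.8% | 6.4% |
| 12 | 6.4% | 9.4% | 12.3% |
| 24 | 12.3% | 17.9% | 23.1% |

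Example: r = 12, d = 2 gives 1 − exp(−24/365) = 0.064.

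As a share of bleeds that trigger escalation over the 45 days from Day 5 to Day 50, divide by 1 − exp(−*r* × 45/365). For the 2-day gap:

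- rate 6: 0.0323/0.523 = 6.2%
- rate 12: 0.0636/0.772 = 8.2%
- rate 24: 0.1232/0.948 = 13.0%

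**5. Rescue endpoint.** FVIIa activity, one of the named candidates, is on the Day 0 list. D-dimer and F1+2 are not. Unscheduled visits (Protocol 8.2.7) may include the markers, but only at the study team's judgement.

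**The case against.** The strongest reply is that the gap is narrow and the safeguard is not empty. Day 0 includes troponin, clinical signs of thrombosis, fibrinogen, TGT, FVIIa activity and MarzAA levels, and a thrombotic event is itself a ground for interrupting dosing. With 12 subjects and a 2-day gap, few will be affected. Passing unsampled through both 60 and 90 µg/kg would happen to about 0.064² = 0.4% of subjects who reach 60 µg/kg at 12 bleeds per year, and 0.123² = 1.5% at 24. That stands, and it limits the size of the point.

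It can also be said that a Day 0 sample may not help the decision. The subject uses his bypassing agent and then calls the site, so many samples will follow rescue. The assays go to a central laboratory with no stated turnaround, while the escalated dose is dispensed at Day 0. Traumatic bleeds, bleeds before the fifth dose and bleeds at 120 µg/kg lead to no escalation, so a Day 0 addition would miss rescue use there. This also stands, but such a sample would still document the level being left and supply what SAP 10.1 and 10.5 assume.

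Finally, the mismatch could be removed by correcting SAP 10.1 instead. That would settle the contradiction but leave the gap.

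A reader might infer three stronger claims that the documents do not support:

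- *That any escalation may lack marker data.* Days 3 and 5 cover the step from 30 µg/kg, and bleeds after the Day 7 draw at higher levels follow at least one on-level sample.
- *That bleeds after Day 28 are judged on outdated markers.* Day 42 has no marker draw, but no passage sets a maximum age for a result.
- *That the rescue endpoint has no planned sample.* FVIIa activity is drawn at Day 0, and SAP 10.1 plans the others.

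**Conclusion.** The point holds in a limited form. The protocol omits D-dimer, F1+2 and TAT from Day 0 in four places, SAP 10.1 assumes they are drawn, and SAP 3.6 contradicts SAP 10.1. Separately, the protocol leaves a gap of about 2 days (3 under Table 4's window, up to 4 under Appendix C's) at 60 and 90 µg/kg in which an escalating bleed has no scheduled marker sample from that level. For the 2-day gap this is roughly a 3%, 6% or 12% chance per level at 6, 12 or 24 spontaneous bleeds per year. These figures rest on a constant rate and on no discretionary sample being taken.

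The cause is the late first draw after escalation combined with the Day 0 omission, not Day 0 alone. For the rescue endpoint, the supportable statement is that the protocol ties no D-dimer, F1+2 or TAT sample to rescue use. No sample size, power or significance level is affected. This is an inexpensive improvement to make, not a flaw that undermines the trial.

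**What to change.** Reconcile Protocol 4.1, Table 4, 8.2.6.1 and Appendix C with SAP 3.6 and 10.1. The preferred route is to add D-dimer, F1+2 and TAT to the blood sample already drawn at Day 0, with a field recording whether it was taken before or after the bypassing agent so that the two groups can be read separately. Where the draw is feasible, this closes the unsampled gap at 60 and 90 µg/kg. If the protocol's list is kept instead, correct SAP 10.1 and state in SAP 10.5 that bleeding-time values of these markers will be sparse.

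Also reconcile the Day 7 window after escalation, which is +1 day in Table 4 and ±2 days in Appendix C.

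The cost is three central-laboratory assays on an existing draw and one data field, with no new visit. The downside is that some values will follow rescue use or be reported after the escalation decision. No dose or escalation rule is changed or proposed.
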